6.2	Intent-to-treat incidence rate ratios comparing product use groups to the control group	18
6.3	Per protocol incidence rate ratios comparing product use groups to the control group	19
6.4	Adjustment for confounding: generalised estimating equation (GEE) models	19
7. A	nalysis of follow-up data: primary safety outcomes	21
7.1	Description of serious adverse events	21
7.2	Description of social harms	21
7.3	Adverse events: structurally assessed at each study visit	21
7.4	Adverse events: not structurally assessed	23
8. A	nalyses of follow-up data: secondary efficacy outcomes	23
8.1	Incidence and incidence rate ratios of secondary efficacy outcomes	23

1. Introduction

This Statistical Analysis Plan (SAP) describes the primary analyses, and one closely related secondary analysis, of the study protocol entitled: "Preparing for a clinical trial of interventions to maintain normal vaginal microbiota for preventing adverse reproductive health outcomes in Africa" (referred to hereafter as the Rwanda VMB Study). The main aim of this study is to determine the safety and preliminary efficacy of three interventions to prevent recurrence of bacterial vaginosis (BV). The study was conducted at Rinda Ubuzima (RU) in Kigali, Rwanda, and was sponsored by the University of Liverpool, Liverpool, UK.

It should be noted that, at the request of the UK Medical Research Council (MRC), the Rwanda VMB Study is a pilot study. Therefore, no formal sample size calculations were done and the sample size was mostly determined by the available budget.

1.1 Study overview

A flow diagram of study visits, and numbers of women seen at each visit, is shown in Figure 1. Women at high risk for HIV, sexually transmitted infections (STIs), and BV were targeted using community mobilisers who were high risk women themselves. Women who were potentially eligible (HIV-negative, non-pregnant, aged 18-45, and sexually active with high risk of HIV/STI/BV) and interested in participating were invited to visit the RU clinic for screening procedures. Please refer to the study protocol for a full listing of eligibility criteria. At the screening visit, a face-to-face interview, speculum examination, and testing for HIV, pregnancy, urinary tract infection (UTI), BV (by Amsel criteria and Nugent scoring), and *Trichomonas vaginalis* (TV; by wet mount and InPouch culture) were conducted. At the end of the visit, preliminary eligibility was assessed, and initial treatments and referrals were given based on available test results. Additional STI testing was conducted on stored samples after the participant had left the clinic. Results of those tests were given as required, and eligibility was reassessed. At the end of the Screening and Results Visits cascade, women were either declared ineligible or diagnosed with BV by Nugent score and/or TV on wet mount or by culture and treated with 500mg oral metronidazole twice per day for 7 days.

At the Enrolment Visit, only women whose BV/TV treatment had been successful (no BV by Amsel criteria and no TV on wet mount), who were still not pregnant, and who were free of STIs and UTI, were randomised to 4 groups as follows:

Group 1) Behavioural 'vaginal practices cessation and safer sex' counselling only (also referred to as the 'control group');

Group 2) Behavioural counselling plus oral metronidazole 500mg, twice per week for two months; Group 3) Behavioural counselling plus Ecologic Femi vaginal capsule, once per day for 5 days immediately after oral metronidazole treatment followed by thrice weekly for two month;

Group 4) Behavioural counselling plus Gynophilus vaginal tablet, once every 4 days for two months. Participants took/inserted the first dose of their intervention (if applicable) under direct observation at the Enrolment Visit.

Participants used their study products (if applicable) for 2 months, and returned for study visits after seven days (D7), one month (M1) and two months (M2; cessation of product use), and then again at six months (M6; 4 months after cessation of product use). At these follow-up visits, participants underwent a face-to-face interview, speculum examination and a variety of laboratory tests (BV by Amsel criteria and Nugent scoring, TV by wet mount and InPouch culture, candidiasis by wet mount, and additional testing if clinically indicated). At the M6 visit, HIV, STI, pregnancy and UTI tests were repeated. Please refer to Table 1 below for a full schedule of assessments by study visit.

Figure 1: Flow diagram of study visits and numbers of women seen at each visit

Table 1: Schedule of assessments

Procedures in clinic during visits	Screening/results	Enrolment	D7, M1, M2	M6
Informed consent	Х	Х		
Contact information	X	Х	X	Х
Assign PIN	X			
Eligibility checklist	X	Х		
Randomisation: initiate interventions		Х		
Cease interventions			X (M2)	
Face-to-face interview, quantitative	X	Х	X	Х
Discussion/interview, qualitative				
Assess AEs and social harms		Х	X	Х
HIV pre- and post-test counselling	X			Х
HIV/STI/BV risk reduction counselling	X	Х	Х	Х
Blood collection (10 ml)	X			Х
Urine collection	X	X		Х
Rapid HIV testing (whole blood) ¹	X			Х
Rapid pregnancy testing (hCG urine)	X	Х	[X]	Х
Rapid UTI testing (urinalysis dipstick)	X	Х	[X]	Х
Speculum exam: visual inspection	X ²	Х	X	Х
Speculum exam: vaginal pH + wet mount (TV,	X ^{2,3}	X ³	X ³	X ³
candida, BV by Amsel ²)				
Speculum exam: vaginal swabs	X	X	X	Х
Speculum exam: endocervical swabs	X ²	Х	[X]	Х
Speculum exam: CVL	X ²	X	X	Х
Provide results and treatment if appl ¹	X	X	X	Х
Laboratory procedures after visits				
Blood: syphilis and HSV-2 serology	Х			X ⁴
Endocervical swab: NG/CT PCR	Х	[X] ⁵	[X] ⁵	Х
Vaginal swabs: TV InPouch culture	Х	X	X	Х
Vaginal swabs: Nugent scoring	Х	Х	Х	Х
Vaginal swabs: store for VMB MiSeq	X	Х	Х	Х
Laboratory procedures if funding permits:	•			
Vaginal swabs: store for additional VMB	X	х	Х	х
assessments (e.g. qPCR, biofilm)				
CVL: store for additional VMB assessments	X	x	X	Х
Vaginal smears: store for biofilm assessments	X	х	X	x

AE=adverse event; BV=bacterial vaginosis; CT=*Chlamydia trachomatis*; CVL=cervicovaginal lavage; D7=Day 7 visit; HPV=human papillomavirus; HSV-2=herpes simplex type 2; M1/2/6=Month 1/2/6 visit; NG=*Neisseria gonorrhoeae*; PIN=participant identification number; qPCR=quantitative PCR; STI=sexually transmitted infection; UTI=urinary tract infection; TV=*Trichomonas vaginalis*; VMB=vaginal microbiome.

1. By the algorithm recommended in the most recent Rwandan HIV voluntary counselling and testing guidelines

2. HIV-positive and pregnant women did not undergo a speculum exam unless clinically indicated but they were asked to donate vaginal swabs for VMB assessments.

3. BV (by Nugent) was always treated during the screening process but was only treated when symptomatic and positive by Amsel score at the Enrolment visit and during follow-up. Candida on wet mount was also only treated when symptomatic. TV on wet mount was always treated.

4. For HSV-2 only when negative at baseline.

5. Endocervical swabs were tested for NG/CT by PCR at screening and M6, but may also be tested at enrolment and/or D7/M1/M2 if deemed necessary for clinical reasons or to accurately interpret the VMB findings.

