5.2 Eligibility criteria

Inclusion criteria:

- Female, 18-45 years old
- Sexually active, defined as having had sex at least twice in the two weeks prior to screening
- At high risk of HIV/STIs/BV, defined as having had more than one sexual partner in the last 12 months OR having been treated for an STI and/or BV in the last 12 months
- Successfully treated for BV by Amsel criteria or TV (defined as no BV by Amsel criteria and no TV on wet mount at the enrolment visit) and free of HIV (at screening), pregnancy (at screening and the enrolment visit), symptomatic vaginal candidiasis and UTI (at the enrolment visit), and syphilis, NG, and CT (at the results visit). Due to the long turn-around time for NG and CT lab test results, women may be enrolled when their NG and CT results are not yet known, but a new participant will be randomised for each woman whose screening sample comes back positive for NG and/or CT after having been randomised. The NG/CT-positive women will be allowed to complete the study but their data may be removed from some analyses.
- Currently in good physical and mental health as judged by a study physician
- Willing and able to adhere to study procedures and provide written informed consent.

According to Rwandan ethics guidelines, unmarried women aged 18-20 also need the written informed consent of a parent or guardian.

 Women are allowed to use contraception, including hormonal contraception; use of these methods will be taken into account in the instructions given to women about probiotic use and in the data analysis.

Exclusion criteria:

- HIV positive
- Pregnant
- Clinician-observed genital ulcers, condylomata, or other genital abnormalities at screening and/or enrolment
- Underwent a gynaecological surgery/invasive procedure in the 3 months prior to screening
- History of significant urogenital prolapse, undiagnosed vaginal bleeding, urine or faecal incontinence, or blood clotting disorders
- Allergic to metronidazole or any other components of the study drugs
- Not willing to stop use of other oral or vaginal probiotics from the screening visit until the end
 of study participation
- Participating in another health intervention study
- For any other reason potentially interfering with participant safety or protocol adherence as judged by the Principal Investigator (these reasons will be recorded)

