6.3 Results visit

All HIV-negative, non-pregnant women regardless of eligibility up to that point will be asked to return to the study clinic 1-2 weeks after the screening visit to obtain their screening test results.

The following procedures will take place at the results visit:

- 1. Confirmation of contact information;
- 2. Provision of HSV-2, syphilis, NG, CT, and TV culture results.
 - If syphilis, NG or CT positive or received treatment for candidiasis at screening (regardless of other test results): Treat STIs according to national guidelines and ask the woman to return to RU as soon as possible after completing her STI treatment for a repeat wet mount. Women who received candidiasis treatment at screening can provide a repeat wet mount at this visit. Vaginal swabs to measure vaginal pH and prepare a wet mount (as well as a slide for Gram stain Nugent scoring) will be obtained without speculum. If negative for BV by Amsel criteria and TV on wet mount, the woman is not eligible for enrolment. If positive for BV by Amsel criteria and/or TV on wet mount, treat using oral metronidazole for 7 days and schedule the enrolment visit within 3 days of completing treatment.
 - If TV culture positive and not yet treated for TV (based on wet mount) at screening: treat using oral metronidazole for 7 days and schedule the enrolment visit within 3 days of completing this treatment.
 - If BV by Amsel criteria at screening and not yet treated (regardless of symptoms): treat using oral metronidazole for 7 days and schedule the enrolment visit within 3 days of completing this treatment.
 - A positive HSV-2 result will not have any treatment or eligibility consequences.
- 3. Due to the logistics of NG/CT PCR, we expect long turn-around time. For this reason, and because the prevalence of NG and CT is much lower than the prevalence of the other STIs, women may be enrolled when their NG and CT results are not yet known. However, a new participant will be randomised for each woman whose screening sample comes back positive for NG and/or CT after having been randomised. The NG/CT-positive women will be allowed to complete the study but their data may be removed from some analyses.
- 4. Due to the logistics of Nugent scoring, Nugent scores may not be available at the enrolment visit. Results will not be used to guide enrolment and treatment decisions anyway, but will only be used in the data analysis.

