6.1 Intent-to-treat incidence rates of primary efficacy outcomes

All women at all study visits were tested for BV by Amsel criteria, BV by Nugent scoring, TV by wet mount, TV by InPouch culture and vaginal candidiasis by wet mount.

During follow-up, antibiotic and antifungal treatments were given as follows:

- BV was only treated when a woman had BV by Nugent score or modified Amsel criteria but also reported symptoms typical for BV (unusual vaginal discharge, fishy smell) or these were observed by the study physician during a pelvic examination. A diagnosis could almost always be made on the day of the study visit.
- TV was always treated when identified on wet mount or by TV culture. The wet mount results were always available on the day of the study visit, but the InPouch culture results only 5 days later. If a woman had tested negative by wet mount but positive by InPouch culture, she was asked to return to the RU clinic for treatment.
- Vaginal candidiasis was only treated when Candida was present on the wet mount and the participant reported symptoms that are typical for vaginal candidiasis (itching, curd-like discharge) or these were observed by the study physician during a pelvic examination. A diagnosis could almost always be made on the day of the study visit.

We will describe any antibiotic or antifungal use between randomisation and M2 and between M2 and M6 by indication, drug type and drug dosing schedule.

Each positive case during follow-up will be assessed separately to differentiate between incident infections and persistent infections. We will assess whether treatments were dispensed appropriately and whether participants adhered to the treatments.

The incidence of each primary outcome will be defined as follows:

- Incident BV by modified Amsel criteria: positive by modified Amsel criteria after having been negative by modified Amsel criteria at the previous visit or after a case of symptomatic BV (diagnosed by modified Amsel criteria or by Nugent score) was adequately treated.
- Incident BV by Nugent score 4-10: a Nugent score of 4-10 after a Nugent score of 0-3 at the previous visit or after a case of symptomatic BV (diagnosed by modified Amsel criteria or by Nugent score) was adequately treated.
- Incident BV by Nugent score 7-10: a Nugent score of 7-10 after a Nugent score of 0-6 at the previous visit or after a case of symptomatic BV (diagnosed by modified Amsel criteria or by Nugent score) was adequately treated.

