- 3. Another special case is the use of antibiotics and/or antifungals during follow-up. If these were prescribed by the study physician due to symptomatic BV, TV, or symptomatic vaginal candidiasis, their use is causally related to the primary endpoints. These women will therefore be included in the per protocol analyses. However, if women used antibiotics and/or antifungals extensively during follow-up, including for reasons not related to the primary endpoints, they may be excluded in the per protocol analyses. This will be determined on a case-by-case basis by the Chief Investigator and each case will be described.

The analyses described in 6.1 and 6.2 will be repeated after exclusion of the participants described in 1, 2, and 3 above. If additional significant protocol deviations are discovered during data analyses (which is unlikely), additional exclusions might be made. These will also be determined on a case-by-case basis and each case will be described.

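### Women culture-positive for TV at Enrolment can be randomised undetected; SAP 6.3 does not exclude them per protocol, and SAP 6.1 counts their person-days from Enrolment

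*SAP*

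**What the plan says.** **Entry.** SAP 1.1 describes women who reached Enrolment as "diagnosed with BV by Nugent score and/or TV on wet mount or by culture and treated with 500mg oral metronidazole" for 7 days. Protocol 6.3 makes culture-only TV an explicit route: "If TV culture positive and not yet treated for TV (based on wet mount) at screening", the woman is treated and scheduled for enrolment.

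**Test of cure.** Protocol 5.2 requires successful treatment, "defined as no BV by Amsel criteria and no TV on wet mount at the enrolment visit". SAP 1.1 repeats this: "only women whose BV/TV treatment had been successful (no BV by Amsel criteria and no TV on wet mount". Neither asks for a negative culture.

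**Enrolment culture.** The row "Vaginal swabs: TV InPouch culture" in SAP Table 1 is marked at Enrolment. SAP 6.1 says wet mount results were available on the day and culture results only 5 days later. It adds: "If a woman had tested negative by wet mount but positive by InPouch culture, she was asked to return to the RU clinic for treatment".

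**Per-protocol set.** SAP 6.3 lists (1) CT or NG infection at randomisation, (2) Nugent 7-10 at Enrolment despite negative modified Amsel criteria, and (3) antibiotic or antifungal use. Then: "The analyses described in 6.1 and 6.2 will be repeated after exclusion of the participants described in 1, 2, and 3 above". Within item 3, women given these drugs by the study physician for symptomatic BV, TV or symptomatic candidiasis stay in, on the ground that this use is causally related to the primary endpoints. A closing clause allows further case-by-case exclusions but calls further deviations unlikely.

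**Incident TV.** SAP 6.1 counts a positive culture after a negative culture at the previous visit, or after an earlier TV case was adequately treated. The denominator is person-days of follow-up, in periods that start at Enrolment or at Month 2.

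**The concern.** For a culture-only entrant, the wet mount was negative before treatment. A negative wet mount after treatment is then weak evidence of cure, and the more sensitive result arrives after she has been randomised.

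SAP 6.3 accepts the principle that an infection present at randomisation but reported later should be removed from the per-protocol analysis. It applies this to CT/NG and to Nugent 7-10, but not to TV by culture, which is itself a primary efficacy outcome.

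Two analyses are exposed:

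- **TV.** The per-protocol set retains women whose TV predates the intervention, and their person-days enter the denominator before they can have an incident infection.
- **BV.** Protocol 3.1 says treatment for TV and BV is identical. If a positive Enrolment culture was treated, that woman received BV-active treatment soon after randomisation, in whichever arm she was, including control.

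**Working it through.** The documents give no figure to reproduce, so the check is mainly textual, followed by an illustration of scale.

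**1. Which result can stop randomisation?**

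| Step | TV test | Stops randomisation? |
|---|---|---|
| Entry (SAP 1.1, protocol 6.3) | wet mount or culture | not applicable |
| Cure (protocol 5.2, 6.4; SAP 1.1) | wet mount | yes, same-day result |
| Enrolment culture (SAP Table 1, 6.1) | culture | no, read 5 days later |

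**2. How does SAP 6.3 treat results that arrive late?**

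| Finding | Sample taken | Result | Per-protocol rule |
|---|---|---|---|
| CT/NG | Screening | usually weeks later | excluded |
| Nugent 7-10 | Enrolment | later | excluded |
| TV culture positive | Enrolment | 5 days later | not listed; kept under item 3 if treated |

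Item 3's reason fails for this woman: treatment for TV already present at Enrolment is not a consequence of anything that happened after randomisation. In the order of procedures in protocol 6.4, the swab is collected before randomisation. Excluding on its result is therefore selection on a baseline finding, as with Nugent 7-10.

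**3. Does she count as an incident TV case at Day 7?** Under the first limb of the definition she does not, because her previous culture was positive. Under the second limb she could, because adequate treatment is not tied to culture and the Screening course might be taken to qualify. Her person-days run from Enrolment either way. By contrast, for NG and CT treated during follow-up, SAP 8.1 starts time at risk at treatment completion.

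**4. How many women?** Expected number = n × f × (1 − s), where n is women entering with TV, f the treatment-failure rate and s the wet-mount sensitivity. Culture is taken as the reference. The documents give none of these inputs for the enrolled women. The low n is guided by the 17% prevalence from an earlier study (protocol 5.1): 0.17 × 68 = 11.56, about 12. The assumed ranges are n = 12 to 30, f = 5% to 20% and s = 40% to 80%.

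| n | f | s | Expected | P(at least one) = 1 − [1 − f(1 − s)]^n |
|---|---|---|---|---|
| 12 | 0.05 | 0.80 | 0.12 | 0.11 |
| 20 | 0.10 | 0.60 | 0.80 | 0.56 |
| 30 | 0.20 | 0.40 | 3.6 | 0.98 |

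These totals cover all four arms. The upper end is 3.6 / 4 = 0.9 per arm.

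**5. Against what denominators?** Of 17 per arm, SAP 6.3 reports 8, 7, 4 and 7 women with CT/NG. Excluding them alone leaves 9, 10, 13 and 10, which is 42 of 68. With equal follow-up, one woman supplies 1/17 = 5.9% of an arm's person-days, or 1/9 = 11% in the smallest per-protocol arm. That is the ceiling on the denominator effect of one such woman within a period; it is smaller if she is treated promptly.

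**The case against.** The case for leaving the SAP alone has real substance.

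- **The numerator is guarded.** SAP 6.1 will review each positive case in follow-up to separate incident from persistent infection, and will check dispensing and adherence. Together with the first limb of the definition, this largely protects the TV case count. A reader might infer that an uncleared Screening infection will be reported as incident at Day 7; the documents do not support that. What remains is that adequate treatment is undefined, and that case review does not touch the person-days or the per-protocol set.
- **No one was randomised untreated.** A reader might infer so, but every woman had 7 days of oral metronidazole. The issue is undetected failure. Nor is the Enrolment wet mount uninformative: a fresh slide can turn positive. It is insensitive for these women.
- **The Nugent side is handled.** Entry on Nugent with cure judged by Amsel raises the same question, but SAP 6.3 discloses the Nugent 7-10 women and excludes them.
- **No case is documented.** The SAP was written with final visit counts in hand, so the missing TV item may mean that there were no cases. The documents do not settle this, and the baseline tables in SAP 4.2 and 4.3 do not show Enrolment culture status by arm.
- **Treatment after a positive Enrolment culture is inferred.** SAP 6.1 describes follow-up, and footnote 3 to SAP Table 1 names only wet mount. Protocol section 6 does say TV is treated at all study visits. The BV consequence depends on this.
- **The stakes are modest.** This is a pilot without a formal sample size, TV is one of five efficacy outcomes, and the GEE models do not use it. That limits the weight of the point but does not remove the inconsistency within SAP 6.3.

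**Conclusion.** The point holds as an inconsistency in the analysis rules. Undetected TV treatment failures can be randomised, and SAP 6.3 as written does not exclude them from the per-protocol set although it removes the parallel CT/NG and Nugent 7-10 cases. The discretionary clause could remove them, but nothing prespecifies it. Item 3 goes further than an omission, since it would retain a treated woman by rule. SAP 6.1 also counts person-days during which she is not at risk of incident TV.

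The size is unknown. On assumed inputs it is about 0.1 to 3.6 women in total, with an 11% to 98% chance of at least one. A reader might instead reckon 68 × 0.17 × 0.30 = 3.5 to 68 × 0.30 × 0.50 = 10.2 women, assuming 17-30% entered with TV and 30-50% of those were wet-mount negative. That counts entrants whose cure test is insensitive, not persistent infections, because no failure rate is applied.

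One misclassified woman matters mainly because the per-protocol arms shrink to between 9 and 13 after the CT/NG exclusion alone. The main BV findings are affected only if such women exist and were treated soon after Enrolment.

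**What to change.** 1. **SAP 6.3:** add a positive TV culture at Enrolment to the listed per-protocol exclusions, beside Nugent 7-10. State that item 3's retention rule does not cover TV already present at Enrolment.
2. **SAP 6.1:** for these women, start TV time at risk at documented completion of treatment given after the Enrolment culture, or at a later negative culture, following the approach of SAP 8.1 for NG/CT. Do not treat the Screening course as adequate treatment when the Enrolment culture is positive. Allowing either starting point keeps a true reinfection after recall treatment countable.
3. **Reporting:** give the number culture-positive for TV at Enrolment in each arm. If it is zero, saying so closes the matter.
4. **Reconciliation:** the passages on entry diagnosis and on test of cure (protocol 5.2 and 6.3, SAP 1.1) should be reconciled. No clinical rule is proposed here.

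The cost is SAP wording and one flag from a culture already in the schedule. The per-protocol set becomes slightly smaller; the set of women in the intent-to-treat analysis is unchanged, apart from the TV time-at-risk correction.
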